#### Patient position:

All patients will be in supine position throughout surgery including induction and emergence of anesthesia. During surgery, all patients will be in steep Trendelenburg at 28 degrees, which is standard for all robotic prostatectomies. This position has been established as optimal for current robotic prostatectomies from the standpoint of the surgical visualization and cardiopulmonary effects intraoperatively

#### Blinding:

Surgeons, patients and those assessing endpoints will be blinded to group assignment. For both arms of the study, black tape will conceal the IAP, so surgeons remain blinded to IAP value throughout the procedure. OR nursing routinely makes adjustments (increase/decrease) at surgeon's direction. Consistent with usual operating room workflow, surgeons will neither adjust the IAP nor have direct visualization of the IAP monitor. The OR nurse will be coached before the procedure to give a scripted response to surgeon's IAP adjustment requests (see Appendix 6). If a surgeon requests notification of actual IAP value during a case, the surgeon will be reminded that the patient is on protocol and value cannot be revealed. Therefore, the starting IAP can be (and will be) adjusted by the surgeon if limitations in visualization will be perceived. If surgeons can assume the value will be either 8, 9, or 10, the possible range of 3 points will adequately blind surgeons for the purposes of this study. There are three timepoints where surgeons may request a specific IAP:

- 1) During initial trochar insertion and insufflation
- 2) During the deep venous catheter dissection
- 3) At conclusion of surgery during hemostasis confirmation

Only at these timepoints can surgeons request an exact IAP. At all other timepoints including immediately preceding and after these timepoints, surgeons will be unaware of IAP and will not be able to infer the IAP based on their request. Additionally, the IAP value will be re-adjusted to the same value as before the change by the surgeon for the above 3 timepoints. At the conclusion of surgery (surgery end time) the surgeon will be asked to give their best guess as to the arm to which the patient had been assigned. This data will be used to evaluate the efficacy of the blinding process.

#### IAP pressure:

IAP (mm Hg) during pneumoperitoneum will be recorded at 15-minute intervals. In addition, IAP will be recorded if there is a pressure change performed regardless of the 15-minute interval. This means, an IAP measurement will be recorded at least once every 15 minutes to ensure that all IAP measurements will be captured within 15 minutes of IAP change. During our pilot, IAP measurements were changed a median of 8 times during robotic prostatectomy.

#### IAP pressure maintenance:

After trocar insertion, the insufflation pressure will be set to a 'starting IAP' value. All cases will begin at this value, which will be less than 10 but above 8 mm Hg. To prevent surgeon bias in initial IAP, the surgeon will not be aware of the starting IAP value. In an effort to partially blind the surgeons to this value, only the range is listed in this protocol (8 to 10), the exact value will be kept private. The blinded start value will be the same for all patients throughout this study. This value will be recorded in the anesthesia record and in the Intraoperative Data Collection Sheet (Appendix 1). As necessary, surgeons will request an increase in pressure to improve visualization. This increase will occur at surgeon's direction, and may increase and decrease per surgeon request with scripted responses from OR nursing (see Appendix 6). Surgeons will remain blinded to the IAP value throughout a case as the value will be concealed with black tape. All surgeon requests to vary IAP will be recorded independent of an actual change in IAP.

#### Surgeon assessment of surgical exposure/visualization:

Overall surgical conditions will be estimated by the surgeon at 30-minute intervals. Our pilot data revealed that the average robotic prostatectomy lasted 5.5 hours. The Leiden surgical rating will be used with a scale of 1-5: 1 being extremely poor conditions and 5 being optimal surgical conditions. This surgical rating scale is well-established for assessing surgeon visualization in laparoscopy,.

#### Estimated blood loss:

Estimated blood loss will be extracted from the electronic medical record (EMR).

#### Postoperative pain (primary endpoint) and postoperative shoulder pain (exploratory endpoint):

The numeric pain scale (NPS) is a subjective measure which can be used in recovery rooms to assist in the assessment of pain. Individuals rate their pain on an eleven-point numerical scale. The scale is composed of 0 (no pain at all) to 10 (worst imaginable pain). Postoperative pain scores are assessed by PACU nurses according to the following scheme:

As per Post Anesthesia Care Unit (PACU) standard of care at Josie Robertson Surgery Center, the PACU nurses that have been trained by the PI and blinded to randomization will ask the patient to rate their pain. The actual question asked is, "on a scale from 0-10, where 0 is no pain and 10 is excruciating pain, please rate

your pain." The pain assessment is administered verbally. PACU nurses ask the patient to rate their pain utilizing the NPS scale. The PACU nurses will be evaluating and assessing pain per the Josie Robertson standard of care by using the Post Anesthetic Discharge Scoring Tool (see Appendix 8). Hour 1 pain scores will be captured from the nursing PACU electronic flowsheet.

Hour 6 and 12 pain scores will be captured in the research assessment form (see Appendix 2).

Most patients on this study will be discharged before 24 hours so assessment at the 24 hour and 48 hour time points will be completed via telephone by the research staff. In the event that the patient has not been discharged from PACU at 24 and 48 hours, the pain scores will be captured in person on the research assessment form.

The 24 and 48 hour time points will be recorded as close to 24 and 48 hours as possible with a +/- 8 hour window to allow for difficulties in reaching patient (see Appendix 2).

Postoperative shoulder pain will be defined at postoperative times of 1-hour, 6-hour, 12-hour, 24-hour and 48-hour on the research assessment form. A pain scale of 0-10 will be utilized (0 = no pain, 10 = worst pain imaginable)

PACU TIME is defined as time of patient arrival to PACU.

Additionally, the total dose of analgesics will be recorded during the intraoperative and the postoperative periods until patient discharge.

Chronic pain patients will be excluded from the protocol. Chronic pain patients are routinely identified by LIP in Presurgical Testing (PST) in advance of surgery. Chronic pain will be defined as a patient on a sustained-release opioid in the last 3 months. To address potential confounding due to a history of chronic pain, analyses of pain-related endpoints will include an adjustment for preexisting chronic pain (yes/no) as a variable.

Patients receiving suboxone will be excluded from protocol.

#### Postoperative nausea:

As per the standard of care at the Josie Robertson Surgery Center, the PACU nurses that have been trained by the PI and blinded to randomization will ask the patient to rate their nausea. The actual question asked is "on a scale of 0-10, where 0 is no nausea and 10 is the worst nausea imaginable, please rate your nausea." The nausea assessment will be administered verbally.

The PACU nurse will record postoperative nausea and vomiting (PONV) in PACU (one-hour post-extubation) and at postoperative times of 1-hour, 6-hour, and 12-hour on the research assessment form., The 24 and 48-hour time points will be completed via telephone by the research staff on the research assessment form if the patient has been discharged before these time points are assessed.

The Apfel 4 point scale for predicting postoperative nausea and vomiting will be used. This scale includes four predictors: female gender, history of motion sickness, nonsmoking, and use postoperative opioids. As all patients in the protocol for robotic prostatectomy will be male, Apfel score will not exceed 3 in any patient. If patient received EMEND preoperatively, the patient will be included in study but the nausea data will be excluded. PONV will be assessed with a scale of 0-10 (0=no nausea and 10 worst nausea imaginable)

In addition, the total dose of rescue antiemetics in the postoperative period will be recorded.

#### RASS scores:

RASS scores will be assessed and collected verbally by the PACU nurse (Hours 1, 6, and 12 post-

operatively). Hour 24 will be collected by phone call. This data will be captured on the research assessment form (see Appendix 2).

#### 4.2 Intervention

A total of 130 patients will be randomized into two groups: deep (intervention) vs. moderate (control) blockade, with 120 patients expected to be evaluable for each of the two endpoints

General anesthesia will be induced as per department routine with minimal variation on induction and maintenance of anesthesia. Upon arrival to the operating room (OR), standard ASA monitors will be applied before induction of anesthesia. All patients will be induced with midazolam (2 mg), propofol (2 mg/kg), fentanyl (1 mcg/kg), lidocaine (1mg/kg), and rocuronium (0.45 mg/kg). This anesthetic regimen will be standardized for both the moderate (control) and deep (intervention) NMB arms.

Patients will receive 100% oxygen during induction of anesthesia. After induction, anesthesia will be maintained at an age-adjusted minimum alveolar concentration (MAC) of 1 with sevoflurane. This will be titrated to maintain a Bispectral index of 35-55. Ventilation will be maintained with tidal volumes of 7 ml/kg, FiO2 less than 50%, and positive end-expiratory pressure (PEEP) and respiratory rate aimed towards normocapnia (ETCO2 of 35-45). For all patients in both arms of the study, two antiemetics (Dexamethasone 4 mg and Ondansetron 4 mg) as well as intravenous acetaminophen (1000 mg) will be administered.

Level of the blockade will be monitored continuously with a TOF GE Anandic NMT device. All patients will be maintained in the same surgical position (angle of Trendelenburg) per robotic urological surgery standard. All surgeons will be blinded to the 'starting IAP' value and all procedures will begin at this value, In addition, IAP value will be recorded at 15-minute intervals. Changes in IAP outside the 15-minute interval measurement point will also be recorded. Increases or decreases in IAP of 1 mmHg per surgeon's request will be allowed throughout the case. Surgical exposure/visualization will be assessed at 30-minute intervals using the Leiden surgical rating scale of 1 to 5 (see Appendices 1 and 3).

Monitoring of neuromuscular block will be in accordance with GE quick guide (see Appendix 8) and it is briefly described below:

Properly secure the sensor of choice (as depicted in Appendix 8). Press measurement start-up. The monitor will start the measurement by setting the stimulus current automatically and by performing a reference measurement. This will be done during induction, before administration of any muscle relaxant. Depolarizing relaxants result in an equal drop in all four responses, without fade. Non-depolarizing relaxants cause a fade in the responses, indicated by a lower TOF% and a slope in the bar graph. Neuromuscular block Is used to facilitate endotracheal intubation. The anesthesia provider can use the time when all responses disappear (i.e., TOF Count is 0) as a guide to determine when to intubate. During surgery, TOF Count is used to maintain a steady optimal level of neuromuscular block. When TOF Count exceeds a level set by the user, the GE monitor will give a "Block recovery" message.

TOF monitoring will occur every minute during the procedure. This will allow for recovery at the neuromuscular junction after post-tetanic stimulation. Administration of additional muscle relaxant will not be allowed. Patients will be maintained in their respective randomized groups (moderate versus deep) and treated unless a change or deterioration in the clinical condition requiring additional muscle relaxant occurs, at which point, such patient will be dropped from the study.

Muscle relaxation will be maintained until abdominal fascia closure, defined as when abdominal incision openings of all port sites are surgically closed. All patients will be reversed using sugammadex as per manufacturer's dosing recommendations: for TOF greater than 2, administer 2 mg/kg; for PTC greater than or equal to 1, administer 4 mg/kg; for PTC of less than 1, investigators will wait until PTC count recovers to 1 and then give 4 mg/kg.. More detailed recommendations are outlined in Appendix 5.

Current standard of care for patients undergoing robotic prostactectomy is moderate blockade (i.e. 1-2 twitches on TOF). Patients in either arm of the study will receive AT LEAST as much blockade as current standard of care. It is extraordinarily unlikely that surgical investigators in this study will demand deeper neuromuscular blockade than a moderate blockade. If a surgeon requests deeper blockade, they will be reminded that the patient is in protocol and that depth of blockade will be at least moderate blockade as per current standard of care. The surgeon will remain blinded to the depth of neuromuscular blockade. In the case a surgeon assesses that deeper blockade is necessary for a given patient, the anesthesia provider will give additional neuromuscular blockade.

Estimated blood loss and total surgical operative time will be extracted from Electronic Medical Record. Postoperatively, endpoints (pain and nausea) will be recorded on all patients by a PACU nurse according to pain and nausea scales. The 24 and 48-hour assessments will be captured via telephone by the research staff. 

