#### 9.0 TREATMENT/INTERVENTION PLAN

[figure not shown]
A total of 130 patients scheduled for robotic prostatectomies will be randomized into two groups: deep (experimental intervention group) versus moderate (control) blockade, with 120 expected to be evaluable for each of the two primary endpoints. In both groups, anesthesia will be induced and maintained per our department's current routine, and standardization will is clearly defined previously in the protocol. For each patient in either arm of the study, recovery from induction dose of rocuronium will be established before reinitiating muscle blockade (deep versus moderate) with rocuronium infusion. Level of the blockade will be monitored continuously with GE Anandic NMT device and dose of rocuronium will be titrated.

All patients will be maintained in the same surgical position (angle of Trendelenburg) per robotic urological surgery standard. All surgeons will be blinded to the 'starting IAP' value and the IAP value will be recorded at 15-minute intervals. Changes in IAP outside the 15-minute interval measurement point will also be recorded. Increases or decreases in IAP per surgeon's request will be allowed throughout the case. Surgical exposure/visualization will be assessed at 30-minute intervals using the Leiden surgical rating scale of 1 to 5. Surgeons will be alerted if IAP reaches 15, which is the standard upper limit of IAP at MSKCC. Investigators request they know the IAP at a level of 15, so they can weigh risk/benefit of continuing to operate at that higher threshold of IAP. At the end of a case, patients in both arms will be reversed with sugammadex at fascia closure. Data will be collected from the of the surgical case. Patients who experience unexpected intraoperative events including death, conversion to open procedure, a decline in clinical condition that would end a planned procedure, anaphylaxis, or a life-threatening hypersensitivity reaction to any medication will be removed from the study.

Estimated blood loss will be recorded from Electronic Medical Record. Postoperatively, endpoints (pain and nausea) will be recorded on all patients by a PACU nurse and research staff(up to 48 hours postoperatively) according to pain and nausea scales as described above. The a PACU nurse will perform these assessments while the patient is on-site. The research nurse will complete 24 and 48-hour assessments by telephone.

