#### 13.0 CRITERIA FOR REMOVAL FROM STUDY

Criteria for removal of subject from the study will include patient death, surgical conversion from robotic to open procedure, intraoperative deterioration in clinical condition that would end a planned procedure.

Patients are considered evaluable for the first primary endpoint (IAP) if they can provide at least one IAP recording; patients are considered evaluable for the second primary endpoint (Pain) if they can provide at least one NPS pain score within 6-hours after surgery. Study data will be analyzed according to a modified intention-to-treat principle ("modified" because patients considered inevaluable for a given primary endpoint will be excluded from the analysis of that endpoint).

The following are a list of possible perioperative scenarios. We expect these to occur extremely infrequently. We anticipate fewer than 10 occurrences during the study period and have planned the protocol accordingly.

- 1) Cancelled surgery
  - Patient will not provide either primary endpoint therefore patients in this category will be excluded from primary analysis
- 2) Patient death
  - For patients who die in the perioperative period, any data up until patient death will be analyzed. These patients may possibly contribute data for only one of the two primary endpoints (IAP)
- Surgical conversion from robotic to open procedure
   Any data up until conversion will be analyzed.

   These patients may possibly contribute data for only one of the two primary endpoints (IAP)
- 4) Intraoperative deterioration in clinical condition that would end planned procedure For patients who experience deterioration in clinical condition that ends planned procedure, any data up until deterioration will be analyzed.
  - However, there will be an investigation to assess the possible (but extraordinarily unlikely) influence of protocol in leading to deterioration.
- 5) Deviation from protocol by giving additional dose of NMB to satisfy surgeon request for better visualization
  - All data in this scenario will be analyzed.. Secondary analysis will be conducted as treated.
- 6) Equipment failure of the neuromuscular train of four monitoring device
  Any data up until failure of neuromuscular train of four monitoring device will be analyzed.patient will
  be considered evaluable for only one of the two primary endpoints (IAP).
- Accidental unblinding of surgeon
   All data will be analyzed.. This will be an evaluable patient.

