#### 10) Monitoring issues

TOF data measured on the GE NMT monitoring device, which currently uses GE's old algorithm, will be sent to GE without randomized arm information to derive corrected TOF (TOFc) based on GE's proprietarty new algorithm. Per correspondence with [name], Principal Engineer at GE Healthcare, he states, "We have made improvements to the TOF algorithm, as its limitations are well known and published. Whereas the old TOF algorithm counted twitches based on their magnitude only, the new algorithm takes both the magnitude and the fade into account. The new algorithm is not published yet and will be in the next Carescape monitor release." Patients with substantial disagreement between TOF and TOFc measurements will be considered as having monitoring issues. Agreement is defined by the proportion of measurements that are perfectly aligned between TOF and TOFc. A second definition for agreement will be the proportion of measurements with a TOF and TOFc difference of <2 twitches. Cases with agreement <80% will be considered a substantial disagreement. We may consider a more stringent threshold for substantial disagreement, for example, agreement <90%.

In addition to those with substantial disagreement between TOF and TOFc (described above), the following patients will also be identified as having monitoring issues:

- 1. Patients with bedside TOF measurements in the operating room but no TOF data available for correction to TOFc
- 2. Patients with incorrect stimulus electrode placement determined by saved images reviewed by GE

Patients with monitoring issues have TOF measurements with varying levels of noise interference, which distinguishes them from patients with, "6) Equipment failure of the neuromuscular train of four monitoring device," which have no TOF measurements. All patients with monitoring issues will be included in the intention-to-treat analyses. Additional analyses based on monitoring issue status are summarized in section 14.0 Study participants that meet the removal criteria above will have their cases reviewed. These cases will be reviewed by an independent panel of surgical and anesthesiology investigators to ensure that the event is not associated with or caused by visibility during the surgery prior to their removal from the study. Any event determined to be due to visibility will be reported to IRB.

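### Section 4.2 drops a patient whose clinical change needs more relaxant: a broader trigger than Sections 9 and 13 use, at odds with the modified intention-to-treat rule, and a possible loss of pain data

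*Combined protocol and SAP*

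**What the plan says.** Section 4.2 bars additional relaxant. It then states an exception: if "a change or deterioration in the clinical condition requiring additional muscle relaxant occurs", the patient leaves, "at which point, such patient will be dropped from the study". It does not say whether leaving means stopping protocol treatment, stopping data collection or exclusion from analysis.

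Two other sections set a narrower limit for clinical decline. Section 9.0 removes for "a decline in clinical condition that would end a planned procedure", and Section 13.0 for "intraoperative deterioration in clinical condition that would end a planned procedure".

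Section 13.0 also defines the modified intention-to-treat principle: "patients considered inevaluable for a given primary endpoint will be excluded from the analysis of that endpoint". One IAP recording makes a patient evaluable for IAP, and one pain score in the first six hours makes a patient evaluable for pain. Item 5 of its scenario list covers "Deviation from protocol by giving additional dose of NMB to satisfy surgeon request for better visualization"; all data are analysed, with a secondary as-treated analysis. Later in Section 4.2 the anesthesia provider may give more block when the surgeon judges it necessary, and no drop is mentioned. Section 14.0 analyses the IAP of moderate-to-deep crossovers in the randomised arm.

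**The concern.** A patient can need more relaxant and still complete the operation. Section 4.2 would drop that patient; Sections 9.0 and 13.0 would not. The trigger is a need for more block, and the arms differ in depth of block, so drops may differ by arm. Section 15.2 gives the anesthesia care team in the operating room access to the assignment, so the people applying the rule are not blinded.

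The two primary endpoints are not equally exposed. IAP is largely safe, because a single recording suffices and recordings begin with insufflation. Pain is collected after surgery, so a drop taken literally could remove the patient from the pain analysis. The case review in Section 13.0 does not clearly act as a safeguard: "Study participants that meet the removal criteria above will have their cases reviewed" refers to that section's own criteria, and this trigger is not among them.

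**Working it through.** **Which rule covers the case?** The case is a clinical change that needs extra relaxant, does not end the operation and is not a surgeon's request for visualization.

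| Rule | What it covers | Covers this case? |
|---|---|---|
| Section 9.0; Section 13.0 item 4 | Decline that ends the procedure (item 4: data up to then analysed) | No |
| Section 13.0 item 5 | Extra dose at surgeon's request; all data kept | Not by its terms |
| Section 14.0 crossover rule | Moderate to deep; recorded IAP | In part; silent on pain and on deep-arm patients |
| Section 13.0 modified intention-to-treat | Excludes only inevaluable patients | Yes in principle, but cannot restore pain scores never collected |
| Section 4.2 | Clinical change needing relaxant | Yes: dropped |

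The only sentence that names the case says drop. The general rules say keep.

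**Inputs for size (Section 14.0).** Pain on the log scale is 1.3 v 0.975, so the difference is 0.325, with SD 0.5. The type I error rate is 0.025 per endpoint. The target is 120 evaluable patients, from at least 130 randomised. Sidedness is not stated; I assume two-sided, z = 2.241.

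**Plan's own figure.** Power = Φ(d / (SD × √(1/n₁ + 1/n₂)) − 2.241). With 60 per arm, the standard error is 0.5 × √(2/60) = 0.0913, and 0.325/0.0913 = 3.560. Power is Φ(1.319) = 0.906, which reproduces the stated 90% for pain alone. IAP alone (2.8/4, 60 per arm) gives 0.944.

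**Loss of k controls.** Let N be the number per arm and let k controls have no pain score, so n₁ = N − k and n₂ = N. For the selective case, I assume those lost average 0.5 SD (0.25) above the control mean. The expected difference becomes 0.325 − 0.25k/(N − k).

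| N per arm | k | Power, no selection | Difference, selective loss | Power, selective loss |
|---|---|---|---|---|
| 65 | 0 | 0.928 | 0.325 | 0.928 |
| 65 | 1 | 0.926 | 0.321 | 0.920 |
| 65 | 3 | 0.922 | 0.313 | 0.900 |
| 65 | 6 | 0.915 | 0.300 | 0.862 |
| 60 | 1 | 0.904 | 0.321 | 0.896 |
| 60 | 3 | 0.898 | 0.312 | 0.871 |
| 60 | 6 | 0.889 | 0.297 | 0.823 |

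Worked line for N = 65, k = 6, no selection: the standard error is 0.5 × √(1/59 + 1/65) = 0.0899; 0.325/0.0899 = 3.615; Φ(1.374) = 0.915.

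The 65-per-arm rows are the right starting point, because 130 are randomised. The 60-per-arm rows apply only if other events have already used the margin of 10 patients.

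**At least one endpoint.** With independence, as the protocol assumes, power is 1 − (1 − 0.944)(1 − 0.906) = 0.995 at 60 per arm. It stays at 0.994 with six controls lost and no selection.

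**The case against.** The strongest reply is that the plan already settles this case through its general rules, and much of that stands. Only inevaluable patients are excluded. Extra doses at the surgeon's request and moderate-to-deep crossovers stay in the randomised arm. Section 14.0 also cites ICH E9 for including patients with post-randomisation violations; that paragraph opens on accidental unblinding, but the principle is worded generally. A reader might therefore infer too much from Section 4.2 in two ways.

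- **That the plan has no data handling for such patients.** It does have general rules, and they favour retention. What is missing is a sentence that names this trigger.
- **That dropped patients are excluded from analysis.** Under Section 13.0, death, conversion and procedure-ending deterioration are removal criteria, yet data up to each event are analysed. Removal there does not mean exclusion.

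Loss of pain data is also uncertain. Section 4.2 has pain recorded for every patient, and hour-1 scores come from the routine PACU flowsheet. Against that, Section 13.0 item 6 treats a patient whose monitor fails as evaluable for IAP only, so leaving the protocol can cost pain evaluability.

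The affected group is narrow. Infusion titration every five minutes corrects ordinary shortfalls in block, and surgeon requests are covered. The documents give no frequency for what remains. The phrase "We anticipate fewer than 10 occurrences during the study period" refers to Section 13.0's own list, which omits this trigger. Nor do they show which arm would lose more patients or in which direction pain would shift.

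**Conclusion.** A minor point that should be corrected. The textual conflict is certain: Section 4.2 states a broader removal than Sections 9.0 and 13.0 and, read literally, contradicts the modified intention-to-treat rule and the handling of surgeon-requested doses. An actual post-randomisation loss of pain data is possible but not established.

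If it occurred at the assumed rates from 65 per arm, pain power would stay at about 92% to 93% without selection and fall to about 86% in the worst selective case shown. The expected difference would then shrink by about 1%, 4% or 8%. The counts of 1, 3 and 6, their restriction to the control arm and the 0.5 SD shift are all assumptions, and the shift could run the other way. The reason to act is that removal may depend on the assigned treatment and is judged by staff who know the arm; the loss of power is secondary.

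**What to change.** In Section 4.2, replace the drop with wording such as: the patient is given the needed relaxant, recorded as a protocol deviation (reason, time and amount), followed for all endpoints including pain, and analysed in the randomised arm with an as-treated secondary analysis. Extend Section 13.0 item 5 to cover a clinical need for extra relaxant as well as a surgeon's request. In the same edit, state that the bar on additional relaxant is a default, subject to the exception that Section 4.2 itself allows later.

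The cost is a sentence of amendment text and a small change to item 5. Intraoperative medications and the rocuronium infusion rate are already on the data list in Section 16.0, so the reason for the dose is the main new item. Sample size, endpoints and models do not change.
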